## 10.5. Appendix 5: Contraceptive Guidance and Collection of Pregnancy Information

#### 10.5.1. Definitions

## Woman of Childbearing Potential (WOCBP)

A woman is considered fertile following menarche and until becoming post-menopausal unless permanently sterile (see below).

If fertility is unclear (eg, amenorrhea in adolescents or athletes) and a menstrual cycle cannot be confirmed before first dose of study intervention, additional evaluation should be considered.

## Women in the following categories are not considered WOCBP

- 1. Premenarchal
- 2. Premenopausal female with one of the following:
  - Documented hysterectomy
  - Documented bilateral salpingectomy
  - Documented bilateral oophorectomy

For individuals with permanent infertility due to an alternate medical cause other than the above, (eg, Mullerian agenesis, androgen insensitivity), Investigator discretion should be applied to determining study entry.

**Note:** Documentation can come from the site personnel's: review of the participant's medical records, medical examination, or medical history interview.

- 3. Postmenopausal female
  - A postmenopausal state is defined as no menses for 12 months without an alternative medical cause prior to the Day 1 Visit.
    - A high follicle stimulating hormone (FSH) level in the postmenopausal range may be used to confirm a postmenopausal state in women not using hormonal contraception or hormonal replacement therapy (HRT). However, in the absence of 12 months of amenorrhea, confirmation with more than 1 FSH measurement may be required. In the absence of 12 months of amenorrhea the reason for not obtaining FSH levels should be documented by the Investigator at the time of Screening.
  - Females on HRT and whose menopausal status is in doubt will be required to use one of the non-estrogen hormonal highly effective contraception methods if they wish to continue their HRT during the study. Otherwise, they must discontinue HRT to allow confirmation of postmenopausal status before study enrollment.
- 4. Permanent sterilization at least 6 weeks prior to the Day 1 Visit.

## 10.5.2. Contraception Guidance

Contraceptive use by male or female participants should be consistent with local regulations regarding the methods of contraception utilized for those participating in clinical studies. If teratogenic effects are suspected to be transferred to a fetus/embryo from a female spouse/partner of a male participant, pregnancy follow-up information will be obtained for the partner who becomes pregnant (refer to Section 10.5.3.1). In these cases, follow-up will be conducted on the pregnant partner in the same manner as a female participant who becomes pregnant during the study.

## 10.5.2.1. Guidance for Female Participants

Female participants of childbearing potential must have a negative pregnancy test ([urine or serum]) as required by local regulations within 3 months before the first dose of study intervention. Additional requirements for pregnancy testing during and after dosing with study intervention are indicated in the SoA (Section 1.3).

The Investigator is responsible for the review of medical history, menstrual history, and recent sexual activity to decrease the risk for inclusion of a woman with an early undetected pregnancy.

The Investigator should evaluate the potential for contraceptive method in relationship to the first dose of study intervention.

Female participants of childbearing potential must use a highly effective method of contraception, including at least 1 of the following until at least 3 months after the final dose of study intervention.

- 1. Intrauterine device in place for at least 6 weeks prior to first dose of study intervention.
- 2. Progestogen-only hormonal contraception associated with inhibition of ovulation (either oral, injectable, or implantable) for at least 6 weeks prior to first dose of study intervention.
- 3. Intrauterine progestogen releasing system for at least 6 weeks prior to first dose of study intervention.
- 4. Bilateral tubal occlusion for at least 6 weeks prior to first dose of study intervention.
- 5. Combined (estrogen- and progestogen-containing) hormonal contraception (either oral, intravaginal, or transdermal) for at least 6 weeks prior to first dose of study intervention.
- 6. Surgical sterilization of the male partner (medical assessment of azoospermia is required if vasectomy was performed within 6 months prior to first dose of study intervention). Male partner is still required to use condom during sexual intercourse.
- 7. Sexual abstinence for female participants:
  - a. Sexual abstinence is considered a highly effective method only if defined as refraining from heterosexual intercourse. In this study, abstinence is only acceptable if consistent with the participant's preferred and usual lifestyle. Abstinent female participants must refrain from heterosexual intercourse for at least 3 months after the final dose of study intervention.

## 10.5.2.2. Guidance for Male Participants

Contraception is the responsibility of the heterosexually active male participants, regardless of his female partner's method of contraception.

Male participants who have had a vasectomy > 6 months prior to the first dose of study intervention must use a condom during heterosexual intercourse. Male participants who have had a vasectomy < 6 months prior to the first dose of study intervention must use a condom and spermicide during heterosexual intercourse for at least 3 months after their final dose of study intervention.

## 10.5.2.2.1. Sexual Abstinence for Male Participants

Sexual abstinence is considered a highly effective method only if defined as refraining from heterosexual intercourse. In this study, abstinence is only acceptable if consistent with the participants' s preferred and usual lifestyle. Abstinent male participants who become heterosexually active must use a condom and spermicide during intercourse.

Periodic abstinence (eg, calendar, symptothermal, or post-ovulation methods for a female partner) is not considered a highly effective method of contraception for male participants.

Male participants must not donate sperm from the Day 1 visit until at least 3 months after the last dose of study intervention.

## 10.5.3. Collection of Pregnancy Information

Pregnancy data will be collected during this study for all female participants and female spouses/partners of male participants. Exposure during pregnancy (also referred to as exposure in utero) can be the result of either maternal exposure or transmission of study intervention via semen following paternal exposure. If a female participant or a male participant's female partner becomes pregnant from the first dose of study intervention up to 3 months after the last dose of study intervention, the Investigator must submit the "Pregnancy/Breastfeeding Reporting and Outcome Form" to Alexion GDS via facsimile or email (Email: \_\_\_\_\_\_\_\_ or Fax: \_\_\_\_\_\_\_\_). When the outcome of the pregnancy becomes known, the form should be updated and submitted to Alexion GDS. If additional follow-up is required, the Investigator will be requested to provide the information.

Exposure of an infant to study intervention during breastfeeding must also be reported (via the "Pregnancy/Breastfeeding Reporting and Outcome Form") and any AEs experienced by the infant must be reported to Alexion GDS or designee via email or facsimile.

Pregnancy is not regarded as an AE unless there is a suspicion that the study intervention may have interfered with the effectiveness of a contraceptive medication. However, complications of pregnancy and abnormal outcomes of pregnancy are AEs and may meet the criteria for an SAE (eg, ectopic pregnancy, spontaneous abortion, intrauterine fetal demise, neonatal death, or congenital anomaly). Elective abortions without complications should not be reported as AEs.

Any female participant who becomes pregnant while participating in the study will be discontinued from study intervention.

## 10.5.3.1. Male Participants With Partners Who Become Pregnant

- The Investigator will attempt to collect pregnancy information on any male participant's female partner who becomes pregnant while the male participant is in this study. This applies only to male participants who receive study intervention.
- After obtaining the necessary signed informed consent from the pregnant female partner directly, the Investigator will record pregnancy information on the appropriate Pregnancy /Breastfeeding Reporting and Outcome Form and submit it to Alexion within 24 hours of learning of the partner's pregnancy. The female partner will also be followed to determine the outcome of the pregnancy. Information on the status of the mother and child will be forwarded to Alexion. Generally, the follow-up will be no longer than 3 months following the estimated delivery date. Any termination of the pregnancy will be reported regardless of fetal status (presence or absence of anomalies) or indication for the procedure.

## 10.5.3.2. Female Participants who become pregnant

- The Investigator will collect pregnancy information on any female participant who becomes pregnant while participating in this study. The initial information will be recorded on the appropriate form and submitted to Alexion within 24 hours of learning of a participant's pregnancy.
- For all Alexion products, both in development or postapproval, exposure during pregnancy must be recorded and the pregnancy followed, until the outcome of the pregnancy is known (ie, spontaneous miscarriage, elective termination, normal birth, or congenital abnormality), even if the participant discontinues the study intervention or withdraws from the study. The Investigator will collect follow-up information on the participant and the neonate and the information will be forwarded to Alexion. Generally, follow-up will not be required for longer than 3 months beyond the estimated delivery date. Any termination of pregnancy will be reported, regardless of fetal status (presence or absence of anomalies) or indication for the procedure.
- Pregnancy is not considered as an AE unless there is a suspicion that the study intervention may have interfered with the effectiveness of a contraceptive medication While pregnancy itself is not considered to be an AE or SAE, any pregnancy complication or elective termination of a pregnancy for medical reasons will be reported as an AE or SAE. A spontaneous abortion (occurring at < 22 weeks gestational age) or still birth (occurring at > 22 weeks gestational age) is always considered to be an SAE and will be reported as such. Any post-study pregnancy related SAE considered reasonably related to the study intervention by the Investigator will be reported to Alexion as described in Section 8.3.4. While the Investigator is not obligated to actively seek this information in former study participants, he or she may learn of an SAE through spontaneous reporting.
- Any female participant who becomes pregnant while participating in the study will be withdrawn from the study.

## 10.6. Appendix 6: Biomarkers

- Blood samples will be collected for biomarker analyses and the data will be used for research (eg, exploratory) related to ALXN1830 and related diseases. The samples may also be used to develop tests/assays including diagnostic tests related to ALXN1830 and/or others of this study drug class.
- The samples may be analyzed as part of a multistudy assessment of biomarkers in the response to ALXN1830 to understand study disease or related conditions.
- The results of biomarker analyses may be reported in the CSR or in a separate study summary.
- Alexion or designee will store the samples obtained for biomarker analyses in a secure storage space with adequate measures to protect confidentiality.
- The samples will be retained while research on ALXN1830 continues but no longer than allowed per local requirements.

## 10.7. Appendix 7: Justification for Protective Measures

The proposed safety measures in this study include documentation of pneumococcal and current seasonal flu vaccination; staggered dosing; stopping rules; close participant monitoring through 60 days after the last dose; close safety and PD monitoring with an unblinded medical monitor; avoidance of participants with a high risk of infections; antibiotics to manage infection as needed; rescue measures such as IVIG replacement in an extremely unlikely event of profoundly low IgG; as well as use of an SRC for safety monitoring and dose selections.

## 10.7.1. IgG Lowering and the Potential Risk of Infection

ALXN1830 is an anti-FcRn mAb that blocks recycling of IgG antibodies, reducing the total IgG in circulation, including potentially pathogenic IgG autoantibodies associated with multiple autoimmune diseases. Thus, reduction in IgG level is used to measure the anti-FcRn PD activity of ALXN1830.

Chronic deficiency of Ig across multiple Ig classes can be associated with an increased risk of infections (eg, in patients with known hypogammaglobulinemia due to primary causes and for secondary reasons due to iatrogenic intervention in patients treated with broadly active therapies, such as rituximab or plasma exchange). For example, rituximab has been documented to widely deplete the B-cell population and affect other Ig classes, while plasma exchange removes all types of serum proteins (Marco, 2014). Likewise, hereditary hypogammaglobulinemia is generally characterized by persistent deficiency of both IgG and other Ig (IgA or IgM) due to inadequate production of gamma globulin. Other immune system disorders, such as common variable immunodeficiency are characterized by lower percentages of memory and isotype switched-memory B cells; increased infection susceptibility; chronic recurrent, persistent infections; and insufficient immune responses to most vaccines, which in turn is also underlined by low levels of IgG and at least 1 other subclass of Ig, such as IgA or IgM documented by laboratory investigations (Filion, 2019).

In contrast to the broadly active agents and immune system disorders discussed above, ALXN1830 is highly specific in reducing IgG in circulation. ALXN1830 has no effect on IgM or IgA levels, and it is also not expected to affect the catabolism of complement, cytokines, or other proteins involved in the immune response, or affect pre-existing cellular immunity (Rath, 2015). Thus, most of the immune system repertoire has been shown to be unaffected by ALXN1830 treatment, maintaining an immunocompetent host. This is supported by prior experience with anti-FcRn therapeutics in healthy participants, which has shown no increase in infection risk despite a significant reduction in tIgG.

The lack of infection risk following anti-FcRn treatment is likely due to both the specificity and transient nature of the IgG reduction, which returns to baseline relatively rapidly after discontinuation of treatment. Specifically, in a single dose and 4-week multiple dose study of the anti-FcRn antibody M281 in healthy participants (n = 50), tIgG was reduced by 85% compared to baseline, and at least 50% of participants experienced a decrease of IgG to < 200 mg/dL over the 2 highest SAD and both MAD cohorts, with no SAEs and few moderate AEs. The incidence of infection-related AEs in this study was similar between the drug-treated groups and PBO, and IgG levels returned to within 20% to 25% of baseline levels within 56 days (Ling, 2019).

Similarly, in a 4-week multiple dose study in healthy participants (n = 62) using the anti-FcRn, efgartigimod, tIgG was decreased on average by approximately 75%, with some individuals showing reductions of up to 85%. There was no increase in infections due to efgartigimod treatment, and IgG levels returned to baseline within 8 weeks after the last dose (Ulrichts, 2018). Also, in a SAD study in healthy participants (n = 48) of the anti-FcRn, rozanolixizumab, IgG levels were reduced by up to 47.6% and returned to baseline within 57 days post dose, with little or no TEAEs reported (Kiessling, 2017). Recently, in a SAD and 4-week MAD study of RVT-1401, total IgG was reduced by up to > 75%, with all AEs being mild to moderate in severity and no participants requiring premature discontinuation due to AEs (Collins, 2019).

Finally, in the previous SAD and MAD studies of ALXN1830 in healthy participants, an IgG lowering of up to 64% was observed (in the 20 mg/kg MAD cohort) with no increased risk of infection, and the IgG levels returned to baseline levels 43 days after the last dose. In total, studies with 5 different anti-FcRn therapeutics (M281, efgartigimod, rozanolixizumab, RVT-1401, and ALXN1830) in well over 200 healthy participants have generally shown no increased risk of infection, and there have been no cases of severe or serious infections reported following anti-FcRn treatment.

In summary, treatment with ALXN1830 is known to lead to a specific reduction of IgG, but not of IgA or IgM, and the IgG lowering is a transient effect with a robust, predictable, and consistent return to baseline in healthy participants. Prior experience with anti-FcRn therapies suggests a low risk of infection even with lowering of IgG to below 200 mg/dL. There have been no cases of severe or serious infections reported following anti-FcRn treatment in healthy participants.

### 10.7.1.1. IgG Level Stopping Rule

The stopping rule based on IgG level of  $\leq$  300 mg/dL was chosen based on generally used classifications of IgG lowering and the prior experience with anti-FcRn treatments discussed above. Classification of reduction in IgG levels has been specified as "mild to moderate" (300 to 600 mg/dL), "significant" (100 to 299 g/dL), or "profoundly reduced" ( $\leq$  100 mg/dL).

Participants with IgG levels of 200 to 400 mg/dL and total Ig level of 400 to 600 mg/dL are considered to have adequate antibody levels to convey humoral immunity, but this is less likely if total Ig levels are less than 400 mg/dL or serum IgG levels are less than 200 mg/dL (Agarwal and Cunningham-Rundles, 2007). Prior experience with anti-FcRn therapeutics in healthy participants showed no increased risk of evidence of infection despite reduction in IgG less than 200 mg/dL. Thus, isolated reduction of IgG to levels as low as 200 mg/dL in the presence of normal IgA and IgM levels and normal cellular elements of immunity (white blood cell [WBC]/differential) would most likely maintain an immunocompetent status. However, to avoid IgG reductions below the mild to moderate range, we will utilize a more conservative level of 300 mg/dL as the threshold for individual and cohort level stopping rules.

To further ensure the IgG nadir would not drop below 300 mg/dL, the inclusion criterion for IgG was set to  $\geq 1000$  mg/dL, higher than the lower limit of normal. Since the proposed dosing regimens of ALXN1830 are not expected to lower IgG levels more than  $\sim 70\%$  as predicted by PK/PD modeling, the IgG levels should remain above 300 mg/dL. Furthermore, the IgG nadir is a transient phenomenon, with IgG levels rising back towards baseline in a relatively rapid timeframe.

Finally, IVIG replacement will be considered only if IgG is profoundly low, ie, below 100 mg/dL, and this low nadir is sustained for more than 7 days despite discontinuation of ALXN1830, which again would be an extremely unlikely event as discussed above.

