#### 4.3. Justification for Dose

Single and multiple IV doses of ALXN1830 have been administered in healthy participants, and in patients with WAIHA and PV. In healthy participants, single IV doses were given at 1, 3, 10 and 30 mg/kg (Study SYNT001-101), and multiple IV doses were given at 20 mg/kg qw for 3 doses and then q2w for 3 doses (Study SYNT001-104). In WAIHA (Study SYNT001-102) and PV (Study SYNT001-103) patients, IV doses of 10 mg/kg qw for 5 doses were given. Also, single SC doses of 750 mg and 1250 mg ALXN1830 have been administered in a limited number of healthy participants (Study ALXN1830-HV-105).

A physiologically based PK/PD model for IV dosing was established and was fitted to the IV PK/PD data from healthy participants. Due to the lack of robust SC data in humans, an SC PK/PD model is not yet available. However, the following has been observed:

- 1. The bioavailability (F) of ALXN1830 after SC administration is likely low:
  - a. Based on the preliminary results from the 5-week SC monkey toxicity study (Study 2455024), F after a single dose of 30 mg/kg SC in monkeys is around 21.5%.
- 2. The maximum reduction of IgG for ALXN1830 is likely similar between IV and SC at the same mg/kg dose:
  - a. At 100 mg/kg IV or SC in the 5-week Good Laboratory Practice (GLP) toxicology studies (Studies 2455-002 and 2455-024), the maximum IgG reduction was 68% after IV and 69% after SC.
  - b. At 750 mg SC or 10 mg/kg IV, similar IgG reduction was observed in a clinical study in healthy participants (Studies ALXN1830-HV-105, SYNT001-01).
- 3. ALXN1830 bioavailability after SC administration is 20%.

Based on these observations, ALXN1830 exposure, safety margin, and IgG reduction after SC administration was predicted (see Table 16). The following assumptions have been used:

ALXN1830 clearance (CL) and body weight have the following relationship:

 $CL = (Median CL) \times (body weight/median body weight)^{0.75}$ 

Table 16: Predicted ALXN1830 Exposure, Safety Margin, and Immunoglobulin G
Reduction after Subcutaneous Administration

Cohort	Dose (mg)	Body Weight (kg) a	Weekly Dose in mg/kg a,b	F	AUC of SC Dosing (h*µg/mL) a.c	Margin Based on NOAEL of Monkey Toxicology Studies a,d	Margin Based on 5-week Monkey SC Toxicology Study a,e	Margin Based on 27-week Monkey IV Toxicology Study a,f	Expected Maximum IgG Reduction (%) g
1	1500,	75	20	0.2	1451	5	4	24	-45

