c AUCSC = (Dose/CLIV) \* F, where CLIV is scaled as CLIV = (Median CLIV) × (body weight/median body weight)0.75. Median CLIV at 10 mg/kg = 239 mL/h with a median body weight of 82.7 kg (SYNT001-101); Median CLIV at 20mg/kg = 215 mL/h with a median body weight of 79 kg (SYNT001-104); Median CLIV at 30 mg/kg = 154 mL/h with a median body weight of 75.8 kg (SYNT001-101). Where median CLIV is not available at certain dose levels (eg 15 mg/kg), doses (mg/kg) are round up to obtain a conservative estimate. Median CLIV for 45 mg/kg is set to equal to median AUCIV at 30 mg/kg (2.03 mL/h/kg). The AUC represents AUC0-inf and AUCss for single and multiple doses respectively.

<sup>d Safety margin = (Monkey NOAEL in mg/kg) / (Human dose in mg/kg). Monkey NOAEL for weekly dosing is 100 mg/kg (Studies 2455-024 and 2455-016).

<sup>e Safety margin = (Monkey AUC0-120h at NOAEL) / (Predicted human AUCSC). Day 29 AUC0-120h =  $6420 \text{ h*}\mu\text{g/mL}$  at 100 mg/kg weekly SC (Study 2455-024).

f Safety margin = (Monkey AUC0-Tlast at NOAEL) / (Predicted human AUCSC). Day 92 AUC0-Tlast = 34800 h\*μg/mL at 100 mg/kg weekly IV (Study 2455-016).

<sup>g IgG reduction is based on predicted IgG reduction at equivalent IV dose in mg/kg. IgG reduction at median body weight is presented.

participant) or 24-fold (for a 75-kg participant) based on the NOAEL exposure from the 27-week IV monkey toxicity study. More importantly, a 30 mg/kg IV single dose has been tested in healthy participants and this starting dose of 1500 mg SC is expected to be roughly one-fifth to one-eighth of the exposure at 30 mg/kg IV, based on the low bioavailability observed in monkeys for ALXN1830 and in healthy participants from other anti-FcRn compounds. Based on these observations, the expected maximum IgG reduction at 1500 mg SC would be around -45% from baseline.

In the SAD portion, the SC dose will be escalated 1.5-fold from 1500 mg (Cohort 1) to 2250 mg (Cohort 2). An SRC review of safety, tolerability, and IgG data will be conducted before each dose escalation. Staggered dosing and pre-specified stopping rules based on safety and IgG reduction will be implemented in all cohorts.

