As shown in Table 16 the first MAD cohort will be administered 750 mg SC qw for 12 weeks (Cohort 3). On a mg/kg basis, the 750 mg SC qw dose represents at least a 7 to 35-fold safety margin when compared to the NOAEL exposures of the 5-week SC and 27-week IV monkey GLP studies. The first MAD cohort (750 mg, qw, Cohort 3) may start at the same time as the single-dose Cohort 1 (1500 mg) while the rest of the MAD cohorts will start after SRC review of the previous MAD cohorts. While all the MAD cohorts have a treatment duration of 4 weeks, Cohort 3 (750 mg SC qw for 12 weeks) is of an extended duration to enable the evaluation of immunogenicity and safety after long term administration of ALXN1830.

The SC multiple doses will be escalated 2-fold from 750 mg qw to 1500 mg qw (Cohort 4), and then 1.5-fold to 2250 mg qw (Cohort 5) after SRC review. At these dose levels, the expected maximum IgG reduction after 4 qw doses is expected to be around 69% and 72%, respectively, which is similar to that observed with 20 mg/kg IV in Study SYNT001-104 (after the 3 qw loading doses).

As shown in Table 15, Cohort 6 will assess the safety, tolerability, PK, PD, safety, and immunogenicity of ALXN1830 in Japanese participants at the highest tolerable dose established in the non-Japanese participants (ie, either up to 1500 mg or up to 2250 mg SC qw for 4 doses). The exact dose and time of dosing will be determined after SRC review of all safety data through Day 36 from Cohort 5 as well as from all prior cohorts. Japanese participants are expected to have a lower mean body weight than non-Japanese participants. This and other differences (eg, genetics) may impact PK/PD in Japanese participants. Although Japanese participants may potentially have slightly higher exposure based on the lower mean body weight, the overall exposure in Japanese participants is predicted not to exceed established safety margins.

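### At 2250 mg weekly × 4 the protocol's own predicted 72% fall gives an IgG nadir of 280 mg/dL at the entry floor, so the 1,000 mg/dL floor does not keep IgG above 300 mg/dL as Section 10.7.1.1 says

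*Protocol*

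**What the plan says.** Protocol Section 10.7.1.1 gives the reason for the IgG entry criterion (at least 1,000 mg/dL, Section 5.1, criterion 4): "To further ensure the IgG nadir would not drop below 300 mg/dL". It argues that the proposed regimens should not lower IgG by more than about 70% and concludes that, "as predicted by PK/PD modeling, the IgG levels should remain above 300 mg/dL". The same figure is the stopping threshold: "we will utilize a more conservative level of 300 mg/dL as the threshold for individual and cohort level stopping rules".

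Section 4.3 gives the predictions by regimen. For 1500 mg and 2250 mg weekly × 4, "the expected maximum IgG reduction after 4 qw doses is expected to be around 69% and 72%, respectively". Table 16 repeats these two values and gives 68% for 750 mg weekly × 12. Footnote g says that the values come from the equivalent IV dose and that "IgG reduction at median body weight is presented".

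Section 7.2.1 states the stopping rules. The individual rule is met when a predose measurement shows IgG at or below 300 mg/dL, and repeat testing is allowed. If two or more participants in a cohort reach that level, dosing in the cohort stops and escalation ends.

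**The concern.** The assurance in Section 10.7.1.1 covers the proposed regimens without exception, yet one of them has a predicted fall larger than the one the assurance rests on. The sentence is the stated reason for an inclusion criterion. If it fails at the top dose, the floor lacks the property claimed for it at the dose where that property matters most.

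Section 10.7.1.1 chose 300 mg/dL so that IgG would not leave the band it calls mild to moderate (300 to 600 mg/dL). A nadir of 280 mg/dL lies in its next band (100 to 299). Someone relying on that section alone would not learn that some eligible participants at 2250 mg weekly are predicted to get there.

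**Working it through.** **Inputs**

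- Entry floor: 1,000 mg/dL (Protocol Section 5.1).
- Level to stay above: 300 mg/dL (Section 10.7.1.1). The stopping threshold is at or below 300 (Section 7.2.1).
- Predicted maximum fall r at median body weight: 68%, 69% and 72% for Cohorts 3, 4 and 5 (Table 16 and Section 4.3).
- Largest fall reported in humans: 64%, at 20 mg/kg IV multiple dose (Section 10.7.1).

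**Formulas**

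Nadir at the floor = 1,000 × (1 − r). Baseline whose nadir is exactly 300 = 300 / (1 − r).

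**The plan's own figure**

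With r = 0.70, 1,000 × 0.30 = 300 mg/dL. This is evidently where the 300 comes from. The floor therefore works only for falls below 70%. At exactly 70% the nadir is 300, which is not above 300.

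**By regimen**

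| Regimen | r | Nadir at floor (mg/dL) | Baseline giving 300 (mg/dL) | Margin to 70% (points) |
|---|---|---|---|---|
| Cohort 3, 750 mg weekly × 12 | 0.68 | 320 | 300/0.32 = 938 | +2 |
| Cohort 4, 1500 mg weekly × 4 | 0.69 | 310 | 300/0.31 = 968 | +1 |
| Cohort 5, 2250 mg weekly × 4 | 0.72 | 280 | 300/0.28 = 1,071 | −2 |
| Largest fall in humans, 20 mg/kg IV | 0.64 | 360 | 300/0.36 = 833 | +6 |

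Edge check at 72%: 1,071 × 0.28 = 299.9 and 1,072 × 0.28 = 300.2. The affected baselines run from 1,000 to about 1,071 mg/dL, a band about 71 mg/dL wide.

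**Rounding of the 72%**

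For r from 0.715 to 0.725, the nadir at the floor runs from 285 down to 275 mg/dL, and the baseline giving 300 runs from 1,053 to 1,091 mg/dL. The conclusion does not change.

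**Timing against the stopping rule**

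Tables 10 and 11 place the Cohort 5 doses on Days 1, 8, 15 and 22. The last predose sample is on Day 22, after three doses. The 72% is the expected maximum after four doses, and the documents give no predicted fall for predose Day 22. Comparing 280 with 300 therefore says something about the nadir, not about whether the individual rule is met.

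**The case against.** The strongest reply is that this is one loosely rounded appendix sentence. The 72% is stated openly in Table 16 and again in the text of Section 4.3, so an investigator, ethics committee or Safety Review Committee (SRC) reading the whole protocol will see it. That is true: nothing is concealed. But loose rounding does not save the sentence, because even an exact 70% leaves no room above 300.

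The 72% is also a soft number. Section 4.3 says "an SC PK/PD model is not yet available", and the figure is carried over from IV dosing. The largest fall reported in humans is 64%, which leaves 360 mg/dL at the floor. (In monkeys at 100 mg/kg, Section 4.3 reports 68% IV and 69% SC.) This stands as a limit on what will happen. It does not rescue the sentence, which itself appeals to prediction.

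The clinical reach is limited too. Section 10.7.1.1 says that people with IgG of 200 to 400 mg/dL, given total immunoglobulin of 400 to 600 mg/dL, "are considered to have adequate antibody levels to convey humoral immunity". The stopping rules remain in force, and the SRC reviews Cohort 4 IgG before Cohort 5 starts. Two qualifications apply. If the nadir follows the fourth dose, no later dose remains for the individual rule to withhold. And the minimum Cohort 4 data in Table 15 run only through Day 22, so they need not contain the nadir after the fourth dose.

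A reader might infer that participants with baselines up to 1,071 mg/dL are predicted to trip the individual stopping rule. The documents do not support that. Section 4.2 summarises the rule without mentioning sample timing, but it refers to Section 7.2, and Section 7.2.1 ties the rule to predose measurements. The cohort rule is not limited to predose samples, but it needs two participants at or below 300.

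**Conclusion.** The point holds, and it is minor. On the protocol's own prediction, the 1,000 mg/dL floor keeps the nadir above 300 mg/dL at 750 and 1500 mg weekly, but not at 2250 mg weekly × 4. There the predicted nadir is 280 mg/dL at the floor, and at or below 300 mg/dL for baselines from 1,000 to about 1,071 mg/dL. Above that baseline the sentence holds at 2250 mg as well.

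This rests on Table 16's point prediction at median body weight, applied as a proportional fall from baseline. No spread between participants is given, so individual falls could be larger or smaller. No distribution of baseline IgG is given either, so neither the share of participants affected nor a stopping probability can be estimated. A reader might also take 280 mg/dL as evidence of an infection hazard. The documents do not show one, and Section 10.7.1.1 treats that level as likely adequate.

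No endpoint or analysis changes. SAP Section 4.1 records early termination with no Cohort 6 participants, so in this trial the practical reach is Cohort 5.

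**What to change.** In Section 10.7.1.1, replace the fall of roughly 70% with up to about 72%. State that at 2250 mg weekly × 4, participants with baseline IgG up to about 1,071 mg/dL have a predicted nadir at or below 300 mg/dL (280 at the floor), so the floor gives the stated protection only at 750 and 1500 mg weekly.

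Make this known to the SRC for the decision on 2250 mg weekly, with a note that the minimum Cohort 4 data through Day 22 need not include the nadir after the fourth dose. Since the trial has ended early, the corrected wording now serves mainly the record and any later protocol that reuses this rationale.

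The change takes a sentence or two and figures that follow directly from Table 16, with no new modelling. The cost is that the reassurance for the top dose becomes less favourable. Whether the floor, the threshold or the dose should change is for the sponsor to decide.
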